8.1.6 Preparation

Available as 500 mg pills

8.1.7 Route of Administration

Capecitabine needs to be taken orally within 30 minutes after a meal

8.1.8 Incompatibilities

N/A

8.1.9 Availability

Commercially available

8.1.10 Side Effects

Hematologic: anemia, neutropenia, thrombocytopenia

Cardiovascular: edema, venous thrombosis
Constitutional: fatigue, pyrexia, swelling in hands, feet or abdomen, pain, chest pain
Dermatologic: hand-foot syndrome, dermatitis, skin discoloration, alopecia
Gastrointestinal: diarrhea, nausea, vomiting, stomatitis, abdominal pain, gastrointestinal motility disorder, constipation, taste disturbance, upper GI inflammatory disorders, gastrointestinal hemorrhage, ileus
Hepatic: hyperbilirubinemia
Infections: bacterial or viral
Metabolic: appetite decreased, dehydration
Musculoskeletal: back pain, arthralgia
Neurologic: peripheral sensory neuropathy, headache, dizziness, insomnia
Ocular: eye irritation, visual abnormalities
Psychiatric: mood alteration, depression
Pulmonary: dyspnea, cough, pharyngeal disorder, epistaxis, sore throat
Vascular: venous thrombosis

8.1.11 Nursing/Patient Implications

- 8.1.11.1 Monitor CBC and platelet count prior to drug administration.
- 8.1.11.2 Symptom management of expected nausea, vomiting, diarrhea, and hand-foot skin syndrome
- 8.1.11.3 Administer doses at least 12 hours (+/- 2 hours) apart.
- 8.1.11.4 Capecitabine pills should be swallowed with water within 30 minutes after a meal.
- 8.1.11.5 Capecitabine pills may not be crushed.

8.2 Temozolomide

8.2.1 Other Names

Temodar

8.2.2 Classification

Cytotoxic chemotherapy, alkylating agent

8.2.3 Mode of Action

Temozolomide [8-carbamoyl-3-methylimidazo(5,1-d)-1,2,3,5-tetrazin-4(3H)-one] (Temodar) is an imidazole tetrazinone compound

developed by Schering-Plough for use as an antineoplastic agent. TMZ is a prodrug that spontaneously hydrolyzes to 5-(3-methyltriazen-1-yl) imidazole-4-carboxamide (MTIC), which is also the active metabolite of dacarbazine. Dacarbazine, however, requires hepatic metabolism for formation of this metabolite, which results in variable levels. TMZ is stable at an acidic pH, allowing oral absorption, and has a broad biodistribution.

Temozolomide is not directly active but undergoes rapid nonenzymatic conversion at physiologic pH to the reactive compound 5-(3-methyltriazen-1-yl)-imidazole-4-carboxamide (MTIC). The cytotoxicity of MTIC is thought to be primarily due to alkylation of DNA. Alkylation (methylation) occurs mainly at the O6 and N7 positions of guanine.

8.2.4 Storage and Stability

As a solid, temozolomide is thermally stable and does not decompose when exposed to light. In solution, temozolomide undergoes rapid hydrolysis in a basic environment. The product label recommends storage at room temperature 25 degrees C (77F). Temozolomide should be stored at 20-25 degrees C (68-77F), excursions permitted between 15-30 degrees C (59-86F).

8.2.5 Dose Specifics

200 mg/m² by mouth once daily on days 10-14 (Arm A)

The temozolomide dose will be capped at 400 mg daily and is available as 5, 20, 100, 140, 180, or 150 mg capsules. The calculated dose by body surface area (BSA) will be rounded down to minimize the number of pills required.

8.2.6 Preparation

N/A

8.2.7 Route of Administration

Oral

8.2.8 Incompatibilities

N/A

8.2.9 Availability

Commercially available

8.2.10 Side Effects

Hematologic: anemia, neutropenia, thrombocytopenia, aplastic anemia

Constitutional: fatigue, anorexia, weight loss

Dermatologic: rash, pruritus, Stevens-Johnson-Syndrome

Gastrointestinal: nausea, vomiting, constipation, diarrhea, abdominal pain, stomatitis, dysphagia

Infusions: PCP infection
Metabolic: hyperglycemia, liver or kidney abnormalities
Neurologic: headache, somnolence, insomnia, blurred vision
Oncologic: secondary malignancy
Psychiatric: anxiety, depression

Rev. 2/17

8.2.11 Nursing/Patient Implications

- 8.2.11.1 Monitor CBC and platelet count prior to drug administration.
- 8.2.11.2 Symptom management of expected nausea, vomiting, photosensitivity, and mucositis within \leq 3 months prior to treatment.
- 8.2.11.3 Ondansetron (or other approved 5HT3 antagonist) will be given as a premedication to prevent nausea 30-60 minutes prior to the temozolomide dose.
- 8.2.11.4 Temozolomide should be taken at night by mouth after fasting from solid food for two hours.
- 8.2.11.5 Temozolomide pills must not be crushed and must be administered whole.
- 8.2.11.6 Temozolomide missed doses will not be made up, and patients should not double-up on missed doses during treatment. Do no repeat dose if vomiting occurs after dose is administered.
- 8.2.11.7 Liver function tests should be performed after each treatment cycle. For patients with significant liver function abnormalities the benefits and risks of continuing temozolomide should be carefully considered.

8.3 Cisplatin

8.3.1 Other Names

Cisdiaminedichloroplatinum, Cis-diaminedichloroplatinum (II), diaminedichloroplatinum, cis-platinum, platinum, Platinol, Platinol-AQ, DDP, CDDP, DACP, NSC 119875.

8.3.2 Classification

Cytotoxic chemotherapy, alkylating agent

8.3.3 Mode of Action

Inhibits DNA synthesis by forming inter- and intra-strand crosslinks. Other possible mechanism include chelation of DNA and binding to cell membranes thereby stimulating immune mechanisms.

	8.3.4	Storage and Stability Intact vials of cisplatin are stored at room temperature. Solutions diluted with sodium chloride or dextrose are stable for up to 72 hours at room temperature. Due to the risk of precipitation, cisplatin solutions should not be refrigerated.
Rev. 2/17	8.3.5	Dose Specifics 25 mg/m ² on days 1-3 of each cycle to be administered per institutional standard. Cycle length is 21 days (Arm B).
Rev. 2/17	8.3.6	Preparation Cisplatin to be mixed per institutional standard.
	8.3.7	Route of Administration Intravenous
	8.3.8	Incompatibilities Amsacrine, cefepime, gallium nitrate, mesna, piperacillin, sodium bicarbonate, thiotepea. Cisplatin may react with aluminum which is found in some syringe needles or IV sets, forming a black precipitate. Compatibilities: Admixture: Amphotericin-B, aztreonam, carmustine, cefazolin, cephalothin, droperidol, etoposide, floxuridine, hydroxyzine, ifosfamide, leucovorin, magnesium sulfate, mannitol, potassium chloride. Y-site: Allopurinol, bleomycin, chlorpromazine, cimetidine, cyclophosphamide, dexamethasone, diphenhydramine, doxapram, doxorubicin, famotidine, filgrastim, fludarabine, fluorouracil, furosemide, ganciclovir, heparin, hydromorphone, lorazepam, melphalan, methotrexate, methylprednisolone, metoclopramide, mitomycin, morphine, ondansetron, paclitaxel, prochlorperazine, ranitidine, sargramostim, vinblastine, vincristine, vinorelbine. Consult your pharmacist regarding specific concentrations.
	8.3.9	Availability Commercially available as a mg/mL solution in 50 and 100 mg vials.
	8.3.10	Side Effects Renal: A dose-related, cumulative renal tubular injury can occur; adequate hydration and diuresis usually minimize the risk. Salt-wasting nephropathy and/or orthostatic hypotension with hyporeninemic hypoaldosteronism can occur in up to 10% of patients. Neurologic: A dose-related ototoxicity, manifested by high-frequency hearing loss and tinnitus occurs in about 30% of patients. Paresthesias, decreased vibratory, position, and touch sensations are less common; particularly at cumulative doses < 400 mg/m ² . Hematologic: mild leukopenia and thrombocytopenia occur in 25-30% of patients, but are rarely dose-limiting; anemia is less common. A potentially fatal hemolytic uremic syndrome has been reported.

Gastrointestinal: severe, dose-limiting nausea and vomiting occur in almost 100% of patients unless adequate antiemetic prophylaxis is given. Even with successful prophylaxis of acute nausea a delayed (72-96 hour) reaction, requiring addition therapy may occur. Anorexia and taste changes may also occur.

Hypersensitivity: allergic reactions are reported in up to 20% of patients. Symptoms include rash, facial edema, wheezing, hypotension and tachycardia. Severe anaphylaxis is rare.

Other: electrolyte wasting (magnesium, potassium and sodium), papilledema, optic neuritis, retrobulbar neuritis, diarrhea, mouth sores, hair loss, dizziness, dehydration, nail changes, fatigue, fluid retention, chills, lowered white blood cell counts, rash, muscle aches, joint pain, headache, confusion, loss of coordination, difficulty swallowing, indigestion, blood clotting in veins, fainting, seizures, difficulty urinating.

Rev. 2/17

8.3.11 Nursing/Patient Implications

- 8.3.11.1 Monitor CBC, platelet count, BUN and creatinine prior to drug administration.
- 8.3.11.2 Monitor for signs of ototoxicity or neurotoxicity.
- 8.3.11.3 Symptom management of expected nausea and vomiting. Ondansetron (or other 5HT3 antagonist) and dexamethasone will be given daily prior to chemotherapy administration. Additional antiemetics may be provided per physician discretion.

If the treating physician chooses to use Aprepitant, when given once daily for 14 days as a 100 mg capsule with an oral contraceptive containing 35 mcg of ethinyl estradiol and 1 mg of norethindrone, this decreased the AUC of ethinyl estradiol by 43% and decreased the AUC of norethindrone by 8%. Women of childbearing potential using pregnancy contraception that includes ethinyl estradiol should not receive Aprepitant for the treatment of nausea/delayed emesis. Patients may change to a different method of contraception if they wish to use Aprepitant.
- 8.3.11.4 Pre- and post-treatment hydration may be administered per institutional standards.
- 8.3.11.5 Diuretics may be ordered as needed per physician discretion.
- 8.3.11.6 Use of granulocyte colony stimulating factors are permitted.
- 8.3.11.7 Observe for signs of allergic reaction.

8.4 Carboplatin

8.4.1 Other Names

Paraplatin®

8.4.2 Classification

Carboplatin (carboplatin injection) (platinum, diammine[1,1-cyclobutanedicarboxylato(2-)O,O']-, (SP-4-2)) is a platinum coordination compound, used as an anti-neoplastic agent. It is a second-generation tetravalent organic platinum compound. It is a crystalline powder with the molecular formula of C₆H₁₂N₂O₄Pt and a molecular weight of 371.25. It is soluble in water at a rate of approximately 14 mg/mL, and the pH of a 1% solution is 5 to 7. It is virtually insoluble in ethanol, acetone, and dimethylacetamide.

8.4.3 Mode of Action

Like cisplatin, carboplatin binds to DNA, thereby inhibiting DNA synthesis, in a cell cycle nonspecific manner. Carboplatin must first undergo activation to produce antineoplastic activity. Bidentate carboxylate ligands of carboplatin are displaced by water forming (aquation) positively charged platinum complexes, which bind to nucleophilic sites in DNA, such as the O-6 position on guanine. Carboplatin produces predominantly interstrand DNA crosslinks rather than DNA-protein crosslinks. Intrastrand crosslinks result from the formation of adducts between the activated platinum complexes of the drug and the N-7 atom (not exclusively) atom on guanine to produce 1,2 intrastrand links between adjacent guanine molecules, between neighboring guanine and adenine molecules, or between neighboring guanine molecules. Interstrand cross-linking within the DNA helix also occurs. Platinum adducts may inhibit DNA replication, transcription and ultimately cell division.

8.4.4 Storage and Stability

Store intact vials at room temperature at 25°C (77°F); excursions permitted to 15°C to 30°C (59°F to 86°F). Protect from light. Further dilution to a concentration as low as 0.5 mg/mL is stable at room temperature (25°C) for 8 hours in NS or D₅W. Stability has also been demonstrated for dilutions in D₅W in PVC bags at room temperature for 9 days; however, the manufacturer recommends use within 8 hours due to lack of preservative. Multidose vials are stable for up to 14 days after opening when stored at 25°C (77°F) following multiple needle entries.

8.4.5 Dose Specifics

Carboplatin will be administered at AUC 5 IV on day 1 every 21 days (3 week cycles).

Calvert Formula for Carboplatin (AUC) Dosing

Total dose (mg) = target AUC (in mg/mL/minute) * GFR (in L/minute) + 25]

For the purposes of this protocol, the GFR is considered to be equivalent to the creatinine clearance.

Glomerular Filtration Rate (GFR) Estimation: Calculated creatinine clearance of \geq 50 cc/min using the Cockcroft-Gault formula:

Males:
$$\frac{(140 - \text{Age in years}) \times \text{Actual Body Weight in kg}}{72 \times \text{Serum Creatinine (mg/dL)}}$$

Females: Estimated creatinine clearance for males x 0.85

With the Calvert formula, the total (final) dose of carboplatin is calculated in mg, not mg/m².

8.4.6 Preparation

Manufacturer's labeling states solution can be further diluted to concentrations as low as 0.5 mg/mL in NS or D₅W; however, most clinicians generally dilute dose in either 100 mL or 250 mL of NS or D₅W. Concentrations used for desensitization vary based on protocol. Hazardous agent; use appropriate precautions for handling and disposal. Needles or IV administration sets that contain aluminum should not be used in the preparation or administration of carboplatin; aluminum can react with carboplatin resulting in precipitate formation and loss of potency.

8.4.7 Route of Administration

Intravenous

8.4.8 Incompatibilities

Amphotericin B cholesteryl sulfate complex. Aluminum reacts with carboplatin causing precipitate formation and loss of potency; therefore, needles or intravenous sets containing aluminum parts that may come in contact with the drug must NOT be used for the preparation or administration of carboplatin.

8.4.9 Availability
Carboplatin (Bristol-Myers Oncology Division) is commercially available in 50, 150, and 450 mg vials.

8.4.10 Side Effects
Hematologic: thrombocytopenia, neutropenia, leukopenia, anemia, more pronounced in patients with compromised renal function and heavily pretreated patients; may be cumulative.
Gastrointestinal: nausea, vomiting, treatable with moderate doses of antiemetics.
Dermatologic: rash, urticaria.
Hepatic: abnormal liver function tests, usually reversible with standard doses.
Neurologic: rarely peripheral neuropathy
Renal: elevations in serum creatinine, BUN; electrolyte loss (Na, Mg, K, Ca).
Other: pain, asthenia.

8.4.11 Nursing/Patient Implications

- 8.4.11.1 Monitor CBC and platelet count; nadir occurs at approximately day 21 with recovery by day 28-30.
- 8.4.11.2 Premedicate with antiemetics—evaluate effectiveness. Ondansetron (or other 5HT3 antagonist) and dexamethasone are required.
- 8.4.11.3 Monitor fluid status—maintain adequate hydration. Pre- and post-treatment hydration may be administered per institutional standards.
- 8.4.11.4 Assess skin/mucous membranes.
- 8.4.11.5 Assess for signs of peripheral neuropathy—coordination, sensory loss.

8.5 Etoposide

8.5.1 Other Names

VP-16, VePesid, VP-16-213, EPEG, epipodophyllotoxin, NSC # 141540.

8.5.2 Classification
Cytotoxic chemotherapy, podophyllotoxin derivative.

8.5.3 Mode of Action
Etoposide inhibits the enzyme topoisomerase II, nucleoside transport and incorporation, and causes DNA breakage.

8.5.4 Storage and Stability
The injection should be stored at room temperature; the capsules must be refrigerated (2-8 degrees C). Following dilution in 0.9% sodium chloride or 5% dextrose to concentrations of 0.2-0.4 mg/mL the drug is chemically stable for 96 and 48 hours in the refrigerator and room temperature respectively (?). Bristol-Myers in-house data indicate that etoposide may be stable in 5% dextrose or normal saline for 24 hours (0.6 mg/mL), 4 hours (1 mg/mL), and 2 hours (2 mg/mL).

8.5.5 Dose Specifics
100 mg/m² on days 1-3 of each cycle per institutional standards. Cycle length is 21 days (Arm B).

8.5.6 Preparation
Etoposide to be prepared per institutional standard.

8.5.7 Route of Administration
Intravenous

8.5.8 Incompatibilities
Etoposide is compatible with cisplatin 200mg/mL in D5½NS or NS for 24 hours when protected from light. Addition of mannitol and/or potassium chloride reduces stability to 8 hours in NS, but remains stable for 24 hours in D5½NS in 5%; also compatible with cytarabine and daunorubicin.

8.5.9 Availability
Commercially available

8.5.10 Side Effects
Hematologic: leukopenia, dose-related, primarily granulocytopenia; nadirs within 7-14 days and recover within 20 days of administration; thrombocytopenia, uncommon; anemia.
Dermatologic: alopecia is generally mild, reversible and is reported to occur in 20-66% of patients although some patients develop total baldness; rarely rash, rarely severe pruritus, rarely radiation recall reaction, phlebitis, local pain at injection site, rarely pigmentation.
Gastrointestinal: nausea and vomiting, relatively uncommon, but more frequent with oral dosing; anorexia in 10-13% of patients; stomatitis, rarely with conventional doses, more common and more severe in patients who have received radiation to the head and neck and with high doses (e.g., bone marrow transplantation); abdominal pain,

diarrhea, aftertaste, parotitis, dysphagia, and constipation occur rarely.

Hypersensitivity: rarely anaphylaxis.

Hepatic: hyperbilirubinemia and increase transaminase levels, usually mild, transient and more common in high dose protocols.

Cardiovascular: transient hypotension, associated with rapid administration; rarely transient hypertension rarely; other cardiovascular events (e.g., congestive heart failure) thought to be related to large amounts of sodium chloride administered with the drug.

Neurologic: peripheral neuropathy, somnolence, fatigue, headache, vertigo, transient cortical blindness (all rarely); transient confusion with high doses, perhaps due to the alcohol-containing vehicle.

Other: rarely fever, muscle cramps, metabolic acidosis, hyperuricemia.

8.5.11 Nursing/Patient Implications

- 8.5.11.1 Monitor CBC and platelet count prior to drug administration.
- 8.5.11.2 Advise patient of possible alopecia. Instruct how to obtain wig, hairpiece, etc.
- 8.5.11.3 Observe for possible phlebitis at injection site or burning pain with infusion.
- 8.5.11.4 Monitor for rare anaphylactoid reaction.
- 8.5.11.5 Administer antiemetics as indicated.

9.1 Endpoints

Primary Endpoint; Progression-Free Survival

Secondary Endpoint; Response Rate, Overall Survival, Toxicity

9.2 Revised statistical plan after Spring 2019 DSMC recommendation (July 2019)

Sample size with power justification

Accrual on this study has been lower than expected, averaging 1-2 patients per month. The ECOG-ACRIN DSMC reviewed this study in Spring 2019 and made the recommendation to modify the statistical plan to reduce the required power of the study to 80% in order to achieve a more realistic sample size and timeframe. Therefore, a total of 80 patients will now be the accrual target to achieve 78 randomized eligible cases. The study seeks to establish an improvement in the primary endpoint, which is defined as a 67% improvement in median progression-free survival (PFS) from 6 months in the control arm (Arm B) to 10 months in the experimental arm (Arm A). The study is now designed to have 80% power for this 40% reduction in the hazard rate with 71 PFS events at full information which is now expected to occur after 75 months of accrual and 7 additional months of follow-up. The primary comparison remains a log-rank test at a one-sided significance level of 0.10. Under exponential distributions the hypothesized reduction corresponds to 1-year progression-free survival of 44% in Arm A versus 25% in Arm B.

Analysis plan including plans for formal interim analysis

The primary analysis set will include all randomized eligible patients. Progression-free survival (PFS) is defined as time from randomization to documented progression or death without progression. Patients without documented progression or death reported will be censored at the time of the last documented disease evaluation. In the secondary analyses, overall survival (OS) is defined as time from randomization to death from any cause, censoring cases who are alive at the date of last contact. Kaplan-Meier estimates will be used for event-time distributions. PFS and OS by arm will be compared using one-sided stratified log-rank tests. Stratified Cox's proportional hazards models will be used to estimate hazard ratios. Response rate (complete response or partial response) and toxicity are also secondary endpoints. Response rate will be analyzed using a Fisher's exact test at a one-sided significance level of 0.10.

Patient demographics and disease characteristics will be compared using two-sample t-tests or Fisher's exact tests as appropriate. We will also conduct exploratory subset analyses with respect to PFS, OS, and response rate to evaluate the prognostic significance of Ki-67 with regard to these clinical endpoints.

Toxicity will be evaluated among all treated patients regardless of eligibility and interim analyses of toxicity are performed twice yearly for all ECOG-ACRIN studies. With 39 eligible patients per arm, the study will have sufficient precision to provide 90% confidence interval on toxicity that will be no wider than 28%. For rare toxicities with 4% true probability, there will be 80% probability of observing

one or more toxicities on either treatment arm. Formal comparison of toxicity rates between the arms is not a goal of this trial and the sample size will provide sufficient power for detecting only relatively large differences in adverse events.

This study will include one interim analysis of PFS for efficacy at approximately 48 months from the start of accrual (possibly near April 2020), which should correspond to 36 failures under the alternative hypothesis or 50% information time). A log rank test using an O'Brien-Fleming boundary will be conducted and under the alternative hypothesis there is probability of 0.29 that the efficacy boundary will be crossed. Regarding futility, if at the interim analysis the estimated hazard ratio for experimental/control is ≥ 1 the study will be reported as negative. If the estimated hazard ratio is less than 1 but the efficacy boundary is not crossed, the study will have its final analysis at 82 months of study. Results of the interim analysis will be presented to the ECOG-ACRIN Data Safety Monitoring Committee (DSMC) when appropriate.

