poorly differentiated) treated with temozolomide and thalidomide, an overall response rate of 25% was observed (45% in pancreatic neuroendocrine tumors, 7% in carcinoids). After a median follow-up period of 26 months, progression free survival and overall survival could not be reported (38). A phase II study of temozolomide and bevacizumab reported a response rate of 15% (33% in pancreatic neuroendocrine tumors, 0% in carcinoids) with an associated median progression free survival of 11.0 months (14.3 months in pancreatic neuroendocrine tumors, 7.3 months in carcinoids) (40). A retrospective study of 30 patients with pancreatic neuroendocrine tumors receiving a combination of temozolomide and capecitabine showed a response rate of 70% with a median progression free survival of 18 months (24). Finally, a small study reporting results of 28/38 planned patients with well differentiated neuroendocrine tumors (including 12 gastrointestinal carcinoid tumors and 11 pancreatic neuroendocrine tumors) receiving temozolomide and capecitabine demonstrates promising results; gastrointestinal carcinoids showed stable disease in 58%, a partial response in 33% and a complete response in 8% with a median progression free survival of > 22 months. In the pancreatic neuroendocrine tumor group, 55% showed stable disease, 45% had a partial response and median progression free survival was >18.2 months (25). These data have established a temozolomide based regimen as a reasonable consideration in the treatment of well differentiated pancreatic neuroendocrine tumors and emerging data suggests that this regimen is efficacious in well differentiated neuroendocrine tumors of non-pancreatic origin as well. To date, no other systemic chemotherapy has shown antitumor activity against both well differentiated and poorly differentiated gastroenteropancreatic neuroendocrine neoplasms.

Rev. 2/17

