4.3 Stratification Factors

Patients will be stratified by the following factors to ensure balance between arms.

4.3.1 ECOG PS 0-1 vs. ECOG PS 2

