4.3.2 GI vs. Pancreatic NET

4.4 Additional Requirements

4.4.1 Patients must provide a signed and dated, written informed consent form.

NOTE: Copies of the consent are not collected by the ECOG-ACRIN Operations Office – Boston.

4.4.2 Biological specimens are to be submitted as indicated in Section [11](#).

4.4.3 Medidata Rave is a clinical data management system being used for data collection for this trial/study. Access to the trial in Rave is controlled through the CTEP-IAM system and role assignments. To access Rave via iMedidata, site staff will need to be registered with CTEP and have a valid and active CTEP-IAM account; and assigned one of the following Rave roles on the relevant Lead Protocol Organization (LPO) or Participating Organization roster at the enrolling site: Rave CRA, Rave Read Only, Rave CRA (LabAdmin), Rave SLA, or Rave Investigator. Refer to <https://ctep.cancer.gov/investigatorResources/default.htm> for registration types and documentation required. To hold Rave CRA role or Rave CRA (Lab Admin) role, the user must hold a minimum of an AP registration type. To hold the Rave Site Investigator role, the individual must be registered as an NPIVR or IVR. Associates can hold read-only roles in Rave.

Upon initial site registration approval for the study in RSS, all persons with Rave roles assigned on the appropriate roster will be sent a study invitation e-mail from iMedidata. To accept the invitation, site users must log into the Select Login (<https://login.imedidata.com/selectlogin>) using their CTEP-IAM user name and password, and click on the “accept” link in the upper right-corner of the iMedidata page. Please note, site users will not be able to access the study in Rave until all

required Medidata and study specific trainings are completed. Trainings will be in the form of electronic learnings (eLearnings), and can be accessed by clicking on the link in the upper right pane of the iMedidata screen. If an eLearning is required and has not yet been taken, the link to the eLearning will appear under the study name in iMedidata instead of the Rave EDC link; once the successful completion of the eLearning has been recorded, access to the study in Rave will be granted, and a Rave EDC link will display under the study name.

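### Response rate is tested with an unstratified Fisher's exact test whose true one-sided size is about 0.06-0.07 rather than the nominal 0.10, giving up roughly 6-11 points of power, nearly all through Fisher's conservatism

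*Combined protocol and SAP*

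**What the plan says.** Section 9.2 (revised plan, July 2019) gives this rule for response rate: "Response rate will be analyzed using a Fisher's exact test at a one-sided significance level of 0.10". It names no stratification. In the same paragraph the time-to-event endpoints are handled differently: "PFS and OS by arm will be compared using one-sided stratified log-rank tests", with hazard ratios from stratified Cox models.

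Section 4.3 says of randomisation: "Patients will be stratified by the following factors to ensure balance between arms". The two factors are "4.3.1 ECOG PS 0-1 vs. ECOG PS 2" and "4.3.2 GI vs. Pancreatic NET".

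On size, Section 9.2 says "a total of 80 patients will now be the accrual target to achieve 78 randomized eligible cases", and the toxicity paragraph works "With 39 eligible patients per arm". Response rate is the first-listed secondary objective (2.2.1) and secondary endpoint (9.1). The plan states no target difference, power or success criterion for it.

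**The concern.** Two features of the response test sit oddly with the rest of Section 9.2. It is the only formal between-arm efficacy comparison there that leaves out the randomisation factors, and no reason is given. It is also a conditional exact test in a small sample. The attainable p-values come in coarse steps, so a nominal 0.10 cannot be fully used.

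What is at stake is power on a formal secondary comparison. The July 2019 revision cut the accrual target from 126 to 80, and Section 1.7 regards a later phase III trial as unlikely. Power that costs no patients is worth having in that setting.

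**Working it through.** **Plan's own power figure (PFS).** With 71 events, hazard ratio 0.6 and one-sided 0.10: √(71/4) × ln(1/0.6) = 2.152; 2.152 − 1.282 = 0.871; Φ(0.871) = 0.808. The stated 80% reproduces. The plan has no corresponding figure for response.

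**Inputs for response.** 39 per arm and one-sided 0.10 come from Section 9.2. Control response rates of 27%, 31% and 42% come from Section 1.3.1. The true differences are assumptions, shown over a range.

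**Why the level is not reached.** With x responders on Arm A, y on Arm B and m = x + y, the one-sided Fisher p-value is P(X ≥ x), X hypergeometric with population 78, m responders and 39 drawn. Take y = 12 (12/39 = 31%). Then x = 18 gives p = 0.122 and x = 19 gives p = 0.082. Nothing lies between, so rejection needs 19.

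**True size.** Let R be the set of the 40 × 40 outcomes with p ≤ 0.10. Size at a common rate π is the sum over R of Bin(x; 39, π) × Bin(y; 39, π).

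| Common response rate | True one-sided size |
|---|---|
| 27% | 0.063 |
| 31% | 0.062 |
| 42% | 0.068 |
| 50% (maximum) | 0.070 |

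**Power, no strata involved.** The same sum with different rates in the two arms, compared with the unstratified pooled z test, over control rates of 27-42%:

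| True difference | Fisher | Pooled z | Loss (points) |
|---|---|---|---|
| +15 points | 0.44-0.45 | 0.53-0.54 | about 9 |
| +20 points | 0.62-0.63 | 0.70-0.71 | about 8.4 |
| +25 points | 0.78 | 0.84-0.85 | about 6.2 |

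The pooled z test can slightly exceed 0.10 (0.106 at 50%, up to 0.12 near 5% or 95%), so part of its gain is not strictly at level 0.10. Boschloo's test is exact and holds 0.10 (maximum size 0.099). For 31% vs 50% it has 66.8% power against 58.8% for Fisher; for 31% vs 46%, 53.1% against 44.3%. That is a gain of 8-9 points with error still bounded. The gain is smaller at a 42% control rate: about 6 points for a 15- or 20-point difference.

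**What the strata add.** The stratified Cochran-Mantel-Haenszel (CMH) statistic is z = Σ(x_k − m_k/2) / √ΣV_k, with equal arms within each stratum k, rejecting at z ≥ 1.2816. Here V_k = n_k² m_k (2n_k − m_k) / [(2n_k)² (2n_k − 1)]. Simulation assumptions: 18 and 17 PS 0-1 patients and 2 and 2 PS 2 patients per arm by site, PS 2 odds halved, treatment odds ratio about 2.2 (31% to 50%).

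| Assumed control rate, GI / pancreatic | Fisher | Unstratified score | Stratified CMH | Due to strata (points) |
|---|---|---|---|---|
| 31% / 31% | 57.6% | 66.4% | 66.5% | 0.1 |
| 20% / 42% | 53.1% | 62.7% | 63.6% | 0.9 |
| 15% / 50% | 46.7% | 57.0% | 60.8% | 3.8 |

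CMH size in these scenarios was about 0.097-0.104. Fisher's size fell to 0.056 and 0.049 in the last two.

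A second set of assumptions used 18/14/4/3 patients per arm across the four strata. The CMH gain over Fisher was 5.6-9.3 points with non-prognostic strata, 6.2-9.8 with moderate and 7.5-10.8 with strong effects (control rates 0.50/0.25/0.20/0.08). Gains above about 11 points arose only with very strong strata or a large PS 2 share.

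**Smaller denominators.** Section 6.1.1 limits response evaluability to patients treated for at least one cycle and re-evaluated, or progressing earlier. With 30-38 per arm, the unstratified loss reaches 11-12.5 points at some combinations.

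**The case against.** A significance level is a ceiling, and Fisher's test respects it. The plan promises no power for response, response is secondary, and the trial's decision rests on PFS. An unstratified exact test in 78 patients is a legitimate conservative choice. The alternative gives up a guarantee: CMH is asymptotic, and two of its four strata might hold about two patients per arm. All of this stands. It makes the point an improvement and not the correction of an error.

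A reader might infer three stronger things that the documents do not support.

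- **That the true error is 0.05 or a little above.** At 39 per arm and the cited rates it is 0.062-0.068. Lower values need low response (about 15% or less), prognostic strata or fewer evaluable patients.
- **That ignoring the strata is the main cause of the loss.** The decomposition shows otherwise: 0.1 and 0.9 points with no or moderate site effect, and 3.8 only under an assumed 15% / 50% split.
- **That the protocol shows a large site effect.** Section 1.4.1 reports "an overall response rate of 25% was observed (45% in pancreatic neuroendocrine tumors, 7% in carcinoids", but that is temozolomide plus thalidomide in 29 patients, 28 of them with well differentiated tumours. For the trial's own regimen the same section gives 33% partial plus 8% complete response (41%) in GI carcinoids against 45% partial response in pancreatic tumours, again in well differentiated disease. No section gives response by site in G3 disease or under platinum, so the contrast cannot size a stratum effect.

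**Conclusion.** The point holds as an efficiency and consistency improvement. The response test runs at a true one-sided size of about 0.06-0.07. It gives up roughly 6-11 points of power for differences of 15-25 points, of which about 0-1.5 come from ignoring the strata under none-to-strong assumed effects. A total of 14 points appears under the assumed 15% / 50% site split and should not be taken as typical.

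The size figures rest on 39 per arm and the cited control rates alone. The power figures also rest on assumed differences, and the stratified ones on assumed stratum sizes and rates. Neither inflated type I error nor a contradicted power statement should be read into this.

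**What to change.** In Section 9.2, replace the Fisher sentence with a one-sided CMH test at 0.10, without continuity correction, stratified by PS (0-1 vs 2) and primary site (GI vs pancreatic) as randomised. Report the stratified response-rate difference with a confidence interval. Name the fallback now: an exact stratified conditional test with mid-p if strata are too sparse. Settle this before outcome data are reviewed.

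The cost is one sentence, with no extra patients or data collection. The downside is a size held only approximately (simulated at about 0.097-0.104), and mid-p is not strictly bounded at 0.10 either (0.106 at a 50% rate when unstratified). If a guaranteed bound matters more than matching the PFS and OS analyses, an unstratified Boschloo test holds 0.10 and recovers most of the power.
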